#### 8.2.5.2 Statistical Methods for Safety Analyses

Safety and tolerability will be assessed by clinical review of all relevant parameters including adverse experiences (AEs), laboratory tests, vital signs, and ECG measurements.

The analysis of safety results will follow a tiered approach ([Table 27](#)) but tier 1 events are not defined in this protocol. The tiers differ with respect to the analyses that will be performed. Membership in Tier 2 requires that at least 4 patients in any treatment group exhibit the event; all other adverse experiences and predefined limits of change will belong to Tier 3. In addition, the broad clinical and laboratory AE categories consisting of the percentage of patients with any AE, a drug related AE, a serious AE, an AE which is both drug-related and serious, and who discontinued due to an AE will be considered Tier 2 endpoints. Tier 2 parameters will be assessed via point estimates with 95% confidence intervals provided for between-group comparisons; only point estimates by treatment group are provided for Tier 3 safety parameters.

The threshold of at least 4 events was chosen because the 95% confidence interval for the between-group difference in percent incidence will include zero when both treatment groups have less than 4 events and thus would add little to the interpretation of potentially meaningful differences. Because many 95% confidence intervals may be provided without adjustment for multiplicity, the confidence intervals should be regarded as a helpful descriptive measure to be used in review, not a formal method for assessing the statistical significance of the between-group differences in adverse experiences and predefined limits of change.

Continuous measures such as changes from baseline in laboratory, vital signs, and ECG parameters will be considered Tier 3 safety parameters. Summary statistics for baseline, on-treatment, and change from baseline values will be provided by treatment group in table format.

Table 27 Analysis Strategy for Safety Parameters

Safety Tier	Safety Endpoint †	p-value	95% CI for Treatment Comparison	Descriptive Statistics
Tier 1	Not defined in this protocol	X	X	X
Tier 2	Any AE		X	X
	Any Serious AE		X	X
	Any Drug-Related AE		X	X
	Any Serious and Drug-Related AE		X	X
	Discontinuation due to AE		X	X
	Specific AEs, SOCs, or PDLCs (incidence $\geq 4$ of patients in one of the treatment groups)		X	X
Tier 3	Specific AEs, SOCs or PDLCs ‡ (incidence $<4$ of patients in all of the treatment groups)			X
	Change from Baseline Results (Labs, ECGs, Vital Signs)			X

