### 3.0 OBJECTIVE(S) & HYPOTHESIS(ES)

### 3.1 Primary Objective(s) & Hypothesis(es)

1) Objective: To assess and compare the safety of MK-5592 and Voriconazole in Japanese subjects with Aspergillosis [Invasive aspergillosis and Chronic pulmonary aspergillosis (Chronic progressive pulmonary aspergillosis and Simple pulmonary aspergilloma)]

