### 5.2.1.2 Dose Modification (Escalation/Titration/Other)

Dose modification of MK-5592 must not be allowed. On the other hand, during the study treatment, measurement of voriconazole concentration in plasma and subsequent TDM is recommended to be performed. The frequency of blood sampling for TDM is judged by the investigator's discretion. Based on the result of voriconazole concentration in plasma, in case of concern about safety and efficacy, dose adjustment of voriconazole should be performed based on the result of TDM, with the dose modified at the investigator's discretion. In case of adjustment of dosage, TDM must be performed. Voriconazole concentration in plasma is recommended between  $\geq 1$ -2  $\mu\text{g}/\text{mL}$  and  $\leq 4$ -5  $\mu\text{g}/\text{mL}$  from efficacy and safety point of view. In this case, upper limit of dosing is 6 mg/kg BID for IV formulation and 300 mg BID for oral formulation. If dose adjustment is performed, voriconazole concentration in plasma should be appropriately monitored after the dose adjustment. Any dose adjustment and voriconazole concentration in plasma should be properly documented in the subject's source documentation and eCRF.

In case of interruption due to adverse event, a temporary interruption of no more than 3 sequential days without study medication will be allowed with resumption of treatment.

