### **7.1.2.11 Domiciling**

Hospitalization is required until all procedures other than study drug administration are completed on Day 9 (9 days and 8 nights after the initiation of study drug). At the discretion of the investigator, subjects may be requested to remain in the investigator's site longer.

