### **7.2.3 Immediate Reporting of Adverse Events to the Sponsor**

#### **7.2.3.1 Serious Adverse Events**

A serious adverse event is any adverse event occurring at any dose or during any use of Sponsor's product that:

- Results in death;
- Is life threatening;
- Results in persistent or significant disability/incapacity;
- Results in or prolongs an existing inpatient hospitalization;
- Is a congenital anomaly/birth defect;
- Is an other important medical event.

**Note:** In addition to the above criteria, adverse events meeting either of the below criteria, although not serious per ICH definition, are reportable to the Sponsor in the same timeframe as SAEs to meet certain local requirements. Therefore, these events are considered serious by the Sponsor for collection purposes.

- Is a cancer;
- Is associated with an overdose.

Refer to [Table 23](#) for additional details regarding each of the above criteria.

For the time period beginning when the consent form is signed until treatment allocation/randomization, any serious adverse event, or follow up to a serious adverse event, including death due to any cause, that occurs to any subject must be reported within 24 hours to the Sponsor if it causes the subject to be excluded from the trial, or is the result of a protocol-specified intervention, including but not limited to washout or discontinuation of usual therapy, diet, placebo treatment or a procedure.

For the time period beginning at treatment allocation/randomization through 14 days following cessation of treatment, any serious adverse event, or follow up to a serious adverse event, including death due to any cause, whether or not related to the Sponsor's product, must be reported within 24 hours to the Sponsor either by electronic media or paper. Electronic reporting procedures can be found in the EDC data entry guidelines. Paper reporting procedures can be found in the Investigator Trial File Binder (or equivalent).

Additionally, any serious adverse event, considered by an investigator who is a qualified physician to be related to the Sponsor's product that is brought to the attention of the

investigator at any time outside of the time period specified in the previous paragraph also must be reported immediately to the Sponsor.

All subjects with serious adverse events must be followed up for outcome.

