### **7.2.4 Evaluating Adverse Events**

An investigator who is a qualified physician will evaluate all adverse events according to the NCI Common Terminology for Adverse Events (CTCAE), version 4.0. Any adverse event which changes CTCAE grade over the course of a given episode will have each change of grade recorded on the adverse event case report forms/worksheets.

All adverse events regardless of CTCAE grade must also be evaluated for seriousness.

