**Table 23 Evaluating Adverse Events**

An investigator who is a qualified physician, will evaluate all adverse events as to:

V4.0 CTCAE Grading	Grade 1	Mild; asymptomatic or mild symptoms; clinical or diagnostic observations only; intervention not indicated.
	Grade 2	Moderate; minimal, local or noninvasive intervention indicated; limiting age-appropriate instrumental ADL.
	Grade 3	Severe or medically significant but not immediately life-threatening; hospitalization or prolongation or hospitalization indicated; disabling; limiting self-care ADL.
	Grade 4	Life threatening consequences; urgent intervention indicated.
	Grade 5	Death related to AE
Seriousness	A serious adverse event is any adverse event occurring at any dose or during any use of Sponsor's product that:	
	† Results in death; or	
	† Is life threatening; or places the subject, in the view of the investigator, at immediate risk of death from the event as it occurred (Note: This does not include an adverse event that, had it occurred in a more severe form, might have caused death.); or	
	† Results in a persistent or significant disability/incapacity (substantial disruption of one's ability to conduct normal life functions); or	
	† Results in or prolongs an existing inpatient hospitalization (hospitalization is defined as an inpatient admission, regardless of length of stay, even if the hospitalization is a precautionary measure for continued observation. (Note: Hospitalization [including hospitalization for an elective procedure] for a preexisting condition which has not worsened does not constitute a serious adverse event.); or	
	† Is a congenital anomaly/birth defect (in offspring of subject taking the product regardless of time to diagnosis); or	
	Is a new cancer; (that is not a condition of the study) or	
	Is an overdose (whether accidental or intentional). Any adverse event associated with an overdose is considered a serious adverse event. An overdose that is not associated with an adverse event is considered a non-serious event of clinical interest and must be reported within 24 hours.	

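### The planned between-arm adverse event summaries have no row by CTCAE grade, so non-serious Grade 3 events with drug continued count the same as Grade 1 events; a cheap addition would show them

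*Combined protocol and SAP*

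**What the plan says.** Section 3.1 gives one primary objective: "To assess and compare the safety of MK-5592 and Voriconazole in Japanese subjects with Aspergillosis". Section 7.2.4 has every AE graded by CTCAE version 4.0 and adds: "Any adverse event which changes CTCAE grade over the course of a given episode will have each change of grade recorded". It treats grade and seriousness as two separate judgements: "All adverse events regardless of CTCAE grade must also be evaluated for seriousness".

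The analysis is in section 8.2.5.2 and Table 27. No Tier 1 events are defined. The broad Tier 2 categories are "the broad clinical and laboratory AE categories consisting of the percentage of patients with any AE, a drug related AE, a serious AE", followed by AEs that are both serious and drug-related and by discontinuation due to an AE. Specific AEs, SOCs and PDLCs join Tier 2 when at least 4 patients in either arm have the event. Tier 2 rows get a between-arm 95% confidence interval; Tier 3 rows get descriptive statistics only. Section 8.2.3.2 refers back to section 7 for the safety endpoints. The visible text has no row by grade, and AEs leading to death are not shown apart from other serious AEs.

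**The concern.** Severity is collected for every event, but the listed between-arm summaries make no use of it. Seriousness and discontinuation stand in for severity only in part, because the protocol allows a severe event to be neither serious nor a cause of stopping drug. Such an event enters the any-AE row, the drug-related row if related, and its specific term and SOC, where it counts as one subject just as a mild event does.

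At stake is what the primary comparison can report. Followed as listed, the plan yields no between-arm estimate for severe AEs as such. It is descriptive and tests no hypothesis (sections 8.2.2 and 8.2.6), so no error rate or decision is at risk.

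**Working it through.** **Step 1: which severe events escape the listed rows.**

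- Table 23 defines Grade 3 as: "Severe or medically significant but not immediately life-threatening; hospitalization or prolongation or hospitalization indicated; disabling; limiting self-care ADL". Much of this overlaps with the seriousness criteria, but limitation of self-care is not by itself one of them.
- The hospitalization criterion in section 7.2.3.1 is: "Results in or prolongs an existing inpatient hospitalization". Section 7.1.2.11 states: "Hospitalization is required until all procedures other than study drug administration are completed on Day 9". During that stay an AE meets this criterion only by prolonging the stay.
- Section 7.1.2.10 asks investigators to treat AEs first and to consider interruption before discontinuation. Section 5.2.1.2 permits "a temporary interruption of no more than 3 sequential days without study medication will be allowed with resumption of treatment".
- Section 5.8 forces discontinuation for QTc above 500 msec, visual problems of Grade 3 or more, exfoliative reactions or suspect skin lesions, Grade 4 AEs related to study drug, and adrenal insufficiency with electrolyte disturbance. These reach the discontinuation row. An unrelated Grade 4 AE is not on that list.
- Death is a seriousness criterion, so fatal AEs are inside the serious row.

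What remains is mainly non-serious Grade 3 AEs, plus any unrelated non-serious Grade 4 AEs, with drug continued.

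**Step 2: reproduce the plan's precision.** Inputs: 60 MK-5592 and 30 voriconazole subjects (section 8.2.7), and the Miettinen-Nurminen method (Table 28). For each candidate difference d, take the maximum-likelihood rates p1 and p2 subject to p1 - p2 = d. The interval is all d for which

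|x1/n1 - x2/n2 - d| / sqrt{[p1(1-p1)/n1 + p2(1-p2)/n2] × N/(N-1)} ≤ 1.96, with N = n1 + n2 = 90.

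In points, MK-5592 minus voriconazole:

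| Counts | 95% CI | Half-width | Table 28 half-width |
|---|---|---|---|
| 6/60 vs 3/30 | -16.8 to 12.5 | 14.6 | 14.6 |
| 9/60 vs 4/30 | -16.4 to 15.9 | 16.1 | 16.1 |
| 12/60 vs 6/30 | -19.5 to 16.3 | 17.9 | 17.9 |

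All three printed half-widths are reproduced. Table 28 prints the limits with the opposite sign.

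**Step 3: precision of a Grade 3 or higher row.** The documents give no Grade 3 rate, so 20% to 40%, equal in both arms, is an assumed range.

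| Assumed rate | Counts | 95% CI | Half-width |
|---|---|---|---|
| 20% | 12/60 vs 6/30 | -19.5 to 16.3 | 17.9 |
| 30% | 18/60 vs 9/30 | -21.0 to 18.8 | 19.9 |
| 40% | 24/60 vs 12/30 | -21.6 to 20.5 | 21.0 |

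The first equals the top of Table 28's range. The others are 19.9 - 17.9 = 2.0 and 21.0 - 17.9 = 3.1 points wider.

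**Step 4: what difference would show.** A half-width at equal rates does not answer this, because the interval depends on the rates and on the direction.

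| Counts | Difference | 95% CI |
|---|---|---|
| 3/60 vs 6/30 | -15.0 | -33.0 to -1.7 |
| 12/60 vs 1/30 | 16.7 | 1.6 to 29.3 |
| 18/60 vs 3/30 | 20.0 | 1.6 to 34.9 |
| 24/60 vs 6/30 | 20.0 | -0.8 to 37.3 |

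A difference of 15 to 17 points can exclude zero, and one of 20 points can fail to.

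**Step 5: contrast with the serious-AE row only.** Assume every serious AE is Grade 3 or higher, and serious AEs occur in 6/60 and 3/30: -16.8 to 12.5, no difference. Add 12 further MK-5592 subjects and no voriconazole subjects with non-serious Grade 3 AEs. Grade 3 or higher becomes (6 + 12)/60 = 18/60 against 3/30, or 30% against 10%: 1.6 to 34.9. The serious row would not show this. If all 12 events fell in one SOC and nothing else did, the planned SOC row would read 12/60 vs 0/30, giving 7.8 to 31.9, and would show it.

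**The case against.** The strongest reply is that nothing here is wrong. The plan is descriptive, and it calls its safety intervals an aid to review. Grade is in the database, so a table by grade can be added later without loss. That stands, and it is why this is a low-severity improvement.

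A second reply is that the gap is small. Section 7.1.2.10 describes most earlier pyrexia, gastrointestinal, hepatic and visual events as mild to moderate, and what escapes is still counted under its specific term and SOC. This also stands in part: only the severity label is lost, and the documents do not give the frequency.

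A reader might infer that the arms could look alike on every listed row and still differ in severe AEs. The example does not show that. It compares one row, and a planned SOC row could reveal the same imbalance unless the events are scattered over several SOCs or offset by lower-grade events in the other arm.

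A reader might also infer that deaths go uncounted. They do not: they are serious AEs, and section 8.2.5.3 displays the primary reason for discontinuation, which may show some of them. A separate count is a display preference. An interval would add little: an assumed 2/60 vs 1/30 gives -13.7 to 8.7.

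Finally, the PDLC limits and the Table 27 footnotes are not in the visible text. PDLCs may cover some severe laboratory changes. The prose list in section 8.2.5.2 does not depend on those footnotes, and nothing visible extends the cover to clinical symptoms.

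**Conclusion.** The point holds as a cheap improvement of low severity. On the visible text, the primary between-arm safety comparison has no summary by grade although grade is recorded for every AE. Non-serious Grade 3 AEs, and unrelated non-serious Grade 4 AEs, with drug continued are then counted like Grade 1 events. How many there will be is unknown.

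A Grade 3 or higher row would have a half-width of 17.9 to 21.0 points at assumed equal rates of 20% to 40%, so it would inform about as well as the rows already planned. This rests on 60 and 30 treated subjects, the Table 28 method, and no grade summary in the footnotes or PDLC definitions that cannot be seen. Sample size, error rates and decision rules are unaffected.

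**What to change.** In section 8.2.5.2 and Table 27:

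- Add any AE of Grade 3 or higher, and any drug-related AE of Grade 3 or higher, to the named broad Tier 2 categories, each with a between-arm 95% confidence interval. Naming them there secures the interval whatever the 4-patient threshold gives.
- Tabulate specific AEs by maximum grade per subject, so that grade changes within an episode are counted once.
- Optionally, report AEs leading to death as a count and percentage by arm, without an interval when events are few.

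The cost is SAP wording and a few table rows from data already on the AE form. There is no new data collection and no change in sample size. The downside is two more unadjusted descriptive intervals, which the existing caution in section 8.2.5.2 already covers.

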### 8.2.7 Sample Size and Power Calculations

This study initially planned to enroll a total of 90 subjects, but due to the modification in protocol such as inclusion and exclusion criteria, an additional 90 subjects will be enrolled as

cohort 2 [redacted]

[redacted]. The cohort 2 will enroll subjects as initially planned for this protocol as follows:

The target number of subjects for the safety analyses will be 90 subjects (MK-5592 treatment arm: 60 subjects, Voriconazole treatment arm: 30 subjects) in this study. From past experiences of the sponsor as well as information of competitors a total number of 90 subjects were set as a target number with consideration of recruitment feasibility.

A total of 90 subjects include subjects with invasive aspergillosis and chronic pulmonary aspergillosis (chronic progressive pulmonary aspergillosis and simple pulmonary aspergilloma). In order to obtain MK-5592 data as much as possible with a limitation of the sample size, the allocation ratio was set 2 to 1. 15 subjects with invasive aspergillosis as a target number will be enrolled. Fusariosis and zygomycosis are very rare deep-seated fungal infections and it is reported that Voriconazole is not effective for treatment of zygomycosis, so subjects with those infections will not be randomized and will be enrolled in the MK-5592 treatment arm without a target number of enrollment.

According to clinical database of Posaconazole Oral Suspension, which is approved and available in the markets of Europe and the United States, as well as clinical studies of MK-5592 in the new formulations up to date, the incident rates of frequently observed adverse experiences (pyrexia, diarrhea, nausea, headache, vomiting and cough) are expected to be approximately 10% - 20%. Assuming that incident rates of the MK-5592 arm and Voriconazole arm are comparable, the half-width of the 95% confidence interval for the difference of the incidence rates will be 14.6% - 17.9% with 60 subjects of the MK-5922 arm and 30 subjects of the Voriconazole arm (Table 28). If a particular adverse experience is not observed in any of the 60 patients in the MK-5592 treatment arm, the true incidence rate for the particular adverse experience is less than 2.6% with 80% confidence. For efficacy assessment, assuming that response rate of 60% (80%), the lower limits of confidence interval for MK-5922 arm will be 46.5% (67.7%) with the sample size of 60.

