Table 28 95% Confidence Interval for Difference of the Incidence Rates for Adverse Events

Incident Rates for both arms (difference of 0%)	95% Confidence Interval		
	Lower Bound	Upper Bound	A half-width of the 95% CI
10%	-12.5	16.8	14.6%
15%	-15.9	16.4	16.1%
20%	-16.3	19.5	17.9%

Incidence Rates for the MK-5592 and Voriconazole treatment arm are assumed to be equal.  
(MK-5592: 60 subjects, Voriconazole: 30 subjects)  
95% confidence interval was calculated with the Miettinen and Nurminen method.

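### The stated reason for the four-patient Tier 2 rule fails at 60 versus 30: 0/60 vs 3/30, and marginally 0/60 vs 2/30, give intervals that exclude zero but are not reported

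*Combined protocol and SAP*

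**What the plan says.** Section 8.2.5.2 sorts adverse events, system organ classes and predefined limits of change into tiers; no Tier 1 events are defined. "Membership in Tier 2 requires that at least 4 patients in any treatment group exhibit the event", and Tier 2 items get a 95% interval for the between-arm difference. Everything else falls to Tier 3, where "only point estimates by treatment group are provided for Tier 3 safety parameters". Table 27 repeats the split, with Tier 3 covering events seen in fewer than four "of patients in all of the treatment groups".

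The reason offered is that the 95% interval for "the between-group difference in percent incidence will include zero when both treatment groups have less than 4 events". No qualification about arm sizes or interval method is attached. The same paragraph says that the intervals are unadjusted and descriptive, "not a formal method for assessing the statistical significance of the between-group differences".

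Section 8.2.7 plans unequal arms: "the allocation ratio was set 2 to 1", giving "MK-5592 treatment arm: 60 subjects, Voriconazole treatment arm: 30 subjects". Section 8.2.5.2 names no interval method. The footnote to Table 28, which covers adverse-event rate differences, says "95% confidence interval was calculated with the Miettinen and Nurminen method".

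**The concern.** The rule withholds an interval because that interval is said to be uninformative. The property claimed is the familiar one for equal arms. With half as many patients on voriconazole, each voriconazole event moves that arm's rate by 3.3 points (1/30) against 1.7 points (1/60) on MK-5592, so a small count on voriconazole with none on MK-5592 can separate the arms.

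A single count also sets two different bars: 4/60 = 6.7% on MK-5592 and 4/30 = 13.3% on voriconazole.

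Comparing safety between the arms is the primary objective (Section 3.1). With no Tier 1 events and no hypothesis test, these intervals are the plan's only inferential comparison of individual adverse events. At stake is whether readers get an interval for an event that appears on voriconazole and not on MK-5592.

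**Working it through.** **Inputs.** Arms of 60 and 30 (Section 8.2.7, Table 28); two-sided 95% level (Section 8.2.5); Tier 2 threshold of four (Section 8.2.5.2); Miettinen-Nurminen interval (Table 28 footnote).

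**Formula.** For a difference d between MK-5592 (1) and voriconazole (2), the limits solve Z(d) = ±1.96, where

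Z(d) = (x1/n1 − x2/n2 − d) / √{ [p1(1−p1)/n1 + p2(1−p2)/n2] × N/(N−1) },

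with p1 and p2 the maximum likelihood estimates restricted to p1 − p2 = d, and N = n1 + n2.

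**Step 1: reproduce Table 28** (its sign is voriconazole minus MK-5592).

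| Counts | Computed limits | Computed half-width | Printed |
|---|---|---|---|
| 6/60, 3/30 | -12.46 to 16.77 | 14.62 | -12.5 to 16.8; 14.6 |
| 9/60, 4/30 | -15.87 to 16.36 | 16.11 | -15.9 to 16.4; 16.1 |
| 12/60, 6/30 | -16.27 to 19.50 | 17.89 | -16.3 to 19.5; 17.9 |

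The 15% row needs 4.5 voriconazole events rounded down to 4. A Wald interval does not reproduce the table (half-widths 13.1, 15.6 and 17.5).

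**Step 2: a hand check at zero.** At d = 0 both restricted estimates equal the pooled rate, so the interval excludes zero when |Z(0)| exceeds 1.96. At 60/30, 1/60 + 1/30 = 0.05 and N/(N−1) = 90/89 = 1.0112.

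- 0/60 vs 3/30: pooled rate 3/90 = 0.0333; variance 0.0333 × 0.9667 × 0.05 × 1.0112 = 0.001629; Z = −0.1000/0.0404 = −2.48. Excludes zero.
- 0/60 vs 2/30: pooled rate 2/90 = 0.0222; variance 0.0222 × 0.9778 × 0.05 × 1.0112 = 0.001099; Z = −0.0667/0.0331 = −2.01. Just excludes zero.
- 1/60 vs 3/30: pooled rate 4/90 = 0.0444; variance 0.002147; Z = −0.0833/0.0463 = −1.80. Includes zero.

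**Step 3: the full grid** of 15 non-empty tables with fewer than four events in both arms (MK-5592 minus voriconazole, in points).

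| Table | Miettinen-Nurminen | Newcombe | Wald upper limit | Fisher p |
|---|---|---|---|---|
| 0/60 vs 3/30 | -25.73 to -3.44 | -25.62 to -1.11 | 0.74 | 0.035 |
| 0/60 vs 2/30 | -21.43 to -0.32 | -21.32 to 1.04 | 2.26 | 0.109 |
| 1/60 vs 3/30 (next closest) | -24.24 to 0.82 | -24.01 to 1.38 | 2.88 | 0.106 |

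Under Miettinen-Nurminen the other 13 tables, 1/60 vs 3/30 among them, include zero. Agresti-Caffo also includes zero for 0 vs 3 (-22.77 to 0.99).

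**Step 4: is allocation the cause?** At 45/45, 3 vs 0 gives -1.55 to 17.94, and no table below four events per arm excludes zero. At ten unequal arm sizes (60/30, 54/27, 56/28, 58/29, 60/28, 58/30, 62/28, 56/32, 64/32, 75/37), 0 vs 3 excludes zero in all ten. 0 vs 2 does so in nine; the exception is 56/32 (-20.25 to 0.50).

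**Step 5: the other direction.** 3/60 vs 0/30 gives -6.66 to 13.77. With no voriconazole events, the interval first excludes zero at 8/60 (1.36 to 24.24), well above the threshold of four.

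**Step 6: how often it would matter.** P(omitted) = P(0 of 60 at rate pM) × [P(2 of 30 at pV) + P(3 of 30 at pV)]. With pV = 10% (assumed), the bracket is 0.2277 + 0.2361 = 0.4637. With pM = 2%, 0.98^60 = 0.298, and the product is 13.8%.

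| MK-5592 rate (voriconazole 10%) | 0% | 0.5% | 1% | 2% | 3% | 5% |
|---|---|---|---|---|---|---|
| Either table | 46.4% | 34.3% | 25.4% | 13.8% | 7.5% | 2.1% |
| 0 vs 3 only | 23.6% | 17.5% | 12.9% | 7.0% | 3.8% | 1.1% |

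With MK-5592 at 2%, the chance is 8.1% for a voriconazole rate of 15% and 3.3% for 20%.

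**The case against.** **Method.** Section 8.2.5.2 names no method, and Miettinen-Nurminen is tied only to a planning table. Under Wald or Agresti-Caffo the sentence would be true. This stands as a limit, but Wald cannot reproduce the plan's own table, and 0 vs 3 also excludes zero by Newcombe and has Fisher p 0.035. The unnamed method is itself a gap.

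**Fragility of 0 vs 2.** It excludes zero by 0.3 points, fails by Newcombe, and fails at 56/32. The score interval is also somewhat liberal at such counts: with both true rates at 2.5%, the chance of none on MK-5592 and two or more on voriconazole is 0.975^60 × (1 − 0.975^30 − 30 × 0.025 × 0.975^29) = 0.219 × 0.172 = 3.8%, against a nominal 2.5% per tail. About half of each omission probability in the 10% table comes from this cell. All of this stands; the firm counterexample is 0 vs 3.

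**Materiality.** Under the plan's own assumption of comparable rates of 10% to 20%, an omission is very rare: about 0.08% per event at 10% and 0.002% at 15%. Tier 3 still shows incidence by arm, the five broad adverse-event categories keep their intervals at any count, and a system organ class or limit of change that reaches four patients keeps its own. No decision depends on an interval excluding zero, and the omissions do not hide an excess on MK-5592. This also stands and bounds the consequence; it does not make the stated reason true.

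**Threshold.** A bar of two on voriconazole admits eight further tables (0 to 3 on MK-5592 with 2 or 3 on voriconazole), six of which include zero. A bar of three would capture the robust case. That is a fair alternative, but under Miettinen-Nurminen the reason would then still be false for 0 vs 2.

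**Conclusion.** The concern holds. At the planned 60/30, and with the only interval method the plan names for adverse-event differences, the justification is wrong for two of the 15 non-empty tables it covers: clearly for 0/60 vs 3/30, marginally for 0/60 vs 2/30. The cause is the 2:1 allocation.

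The effect is confined to events nearly absent on MK-5592 and uncommon to moderately common on voriconazole. The omission probabilities rest on assumed true rates and on arms of exactly 60 and 30. No hypothesis test, decision rule or broad safety category changes. It is worth correcting because the sentence governs which individual events receive a comparison under the primary objective, and the correction is small.

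**What to change.** In Section 8.2.5.2 and Table 27:

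1. Name Miettinen-Nurminen as the method for the between-arm adverse-event intervals.
2. Define Tier 2 as at least four patients on MK-5592 or at least two on voriconazole (4/60 = 2/30 = 6.7%), with Tier 3 as the complement.
3. Replace the reason with one that is true here: under 2:1 allocation the interval includes zero when fewer than four MK-5592 patients and fewer than two voriconazole patients have the event. This was checked for every such table at 60/30 and at the nine other unequal arm sizes listed in the working.

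The cost is a paragraph, a table and more unadjusted descriptive rows, including some chance exclusions against voriconazole. If the true rates are equal, 0 vs 2 or 0 vs 3 occurs with probability 2.0% per event at a rate of 1%, 3.5% at 2% (2.9 points of it from 0 vs 2) and 1.8% at 5%. The plan's existing caution about unadjusted intervals already covers these rows. If the sponsor prefers to keep the threshold of four, the minimum is to name the method and withdraw the claim that the omitted intervals always include zero.

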#### **8.2.5 Statistical Methods**

The main objective of this study is assessment of safety and the formal hypothesis testing for efficacy endpoints will not be conducted. Nominal p-values and confidence intervals will be presented at the  $\alpha=0.05$  (2-sided) level.

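### Changes from baseline in laboratory, ECG and vital-sign values get by-arm summaries but no between-arm interval, although comparing safety between arms is the primary objective

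*Combined protocol and SAP*

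**What the plan says.** The one primary objective (section 3.1) is "To assess and compare the safety of MK-5592 and Voriconazole in Japanese subjects with Aspergillosis". Section 8.2.2 sets no hypothesis, so the comparison rests on estimates and intervals.

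Section 8.2.5.2 sorts safety measures into tiers:

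- **Tier 1** is empty in this protocol.
- **Tier 2:** "Tier 2 parameters will be assessed via point estimates with 95% confidence intervals provided for between-group comparisons". It holds the broad AE categories (any, drug-related, serious, both, discontinuation due to AE) and those specific AEs, organ classes or predefined limits of change (PDLCs) that are frequent enough: "Membership in Tier 2 requires that at least 4 patients in any treatment group exhibit the event".
- **Tier 3:** "only point estimates by treatment group are provided for Tier 3 safety parameters". Continuous changes from baseline are assigned here: "Continuous measures such as changes from baseline in laboratory, vital signs, and ECG parameters will be considered Tier 3 safety parameters". They are reported as follows: "Summary statistics for baseline, on-treatment, and change from baseline values will be provided by treatment group in table format".

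Table 27 agrees. The row beginning "Change from Baseline Results (Labs, ECGs, Vital Signs" has a single mark, which the text places under descriptive statistics and not under the CI for treatment comparison. The general sentence in section 8.2.5 ("Nominal p-values and confidence intervals will be presented at the" two-sided 0.05 level) does not override the tier rule.

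**The concern.** Chemistry and vital signs are scheduled at every visit, and ECGs at screening, Days 1, 3, 8 and 42, end of treatment, formulation switch and follow-up (section 6.0). The protocol treats some of these values as important: QTc has an entry limit and a discontinuation limit (sections 5.1.3 and 5.8), and a combination of liver tests is an event of clinical interest (section 7.2.3.2). Under the tier rule, none of them is compared between arms on its own scale. A difference in QTc, ALT or creatinine reaches an interval only after it has become an AE or crossed a PDLC.

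The plan explains why it withholds intervals: with fewer than 4 events in both arms, the CI for the incidence difference would include zero and add little. That argument is about sparse counts. A mean change measured in nearly every subject is not sparse, and no other reason is given for leaving it without an interval. The risk is that a moderate shift affecting most subjects goes unquantified in the comparison the trial was set up to make.

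**Working it through.** **Inputs.** 60 MK-5592 and 30 voriconazole subjects; Miettinen-Nurminen intervals; AE rates of 10-20% (all section 8.2.7 and Table 28); two-sided 5% (section 8.2.5). Assumptions not in the documents: normally distributed changes in SD units; a shift of 0.5 SD in every MK-5592 subject, up or down; a cut exceeded by 10% or 20% of voriconazole subjects; correlation 0.5 for the baseline adjustment.

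**1. The plan's own figure.** The Miettinen-Nurminen half-width is 14.62 points for 6/60 v 3/30, 16.11 for 9/60 v 4/30 (4.5 events rounded down) and 17.89 for 12/60 v 6/30. Table 28 prints 14.6, 16.1 and 17.9, so it reproduces.

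**2. Mean difference.** SE = SD × √(1/60 + 1/30) = 0.2236 SD. With t(0.975, 88 df) = 1.987, the 95% CI half-width is 0.444 SD. For a 0.5 SD shift the noncentrality is 0.5/0.2236 = 2.236, and the CI excludes zero in 60% of trials.

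**3. With baseline adjustment.** The residual SD is √(1 − 0.5²) = 0.866. The shift becomes 0.5/0.866 = 0.577 residual SD, the noncentrality 2.582, and the CI excludes zero in 72% of trials.

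**4. The same variable after a cut.** If voriconazole subjects exceed the cut at rate p, the MK-5592 rate is 1 − Φ(z(1−p) − shift). The score statistic is z = (x₁/60 − x₂/30) / √[p̄(1 − p̄)(1/60 + 1/30)(90/89)], and its power was summed exactly over both binomials.

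| Cut | Shift | MK-5592 rate | CI excludes zero |
|---|---|---|---|
| 10% | +0.5 SD | 21.7% | 26% |
| 10% | −0.5 SD | 3.7% | 23% |
| 20% | +0.5 SD | 36.6% | 36% |
| 20% | −0.5 SD | 9.0% | 33% |

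Other shifts, cut v mean difference v adjusted: 17-25% v 42% v 53% at 0.4 SD; 30-50% v 76% v 87% at 0.6 SD.

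**5. The 4-patient rule.** For a PDLC with the same true rate in both arms, P(interval shown) = 1 − P(X₁ ≤ 3) × P(X₂ ≤ 3). At 5% this is 1 − 0.647 × 0.939 = 39%; at 10%, 1 − 0.137 × 0.647 = 91%; at 2%, 3%. In step 4, applying the rule lowers the 10% cut at −0.5 SD from 23% to 19%.

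**6. When only a minority react.** Simulation with a fraction of MK-5592 subjects having a large rise, and a cut exceeded by 2% under no effect:

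| Fraction and rise | t-test, unequal variances | Cut |
|---|---|---|
| 10%, 3 SD | 21% | 15% |
| 15%, 3 SD | 40% | 42% |
| 15%, 4 SD | 53% | 56% |

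With a pooled-variance t-test the last two rows fall to about 29% and 38%, clearly below the cut. The advantage in steps 2-4 therefore belongs to shifts shared by most subjects.

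**The case against.** The strongest defence is that this is an explicit, coherent choice. No hypothesis is set, the plan calls its intervals descriptive, and reporting continuous safety data by arm contradicts nothing. Judging the plan by how often a CI excludes zero also borrows a testing standard that it disclaims. Much of this stands: the point is a gap in estimation, not an error, and the percentages above only convey relative precision. But the plan already uses descriptive between-arm intervals for its safety comparison, and its reason for stopping short of them does not reach continuous data.

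Several stronger readings are tempting and are not supported:

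- *That the plan discards these data.* Section 8.2.5.2 summarises them by arm and includes them in the clinical review. A reader with mean, SD and n could derive an unadjusted interval, though not the baseline-adjusted one.
- *That every interval is subject to the 4-patient rule.* The broad AE categories are exempt, and an abnormal laboratory finding can count as an AE (section 7.2).
- *That the cut measures ignore baseline.* PDLCs are by name limits of change, and the available text does not define them.
- *That the continuous scale is always the more sensitive.* Step 6 shows otherwise. The protocol's own QTc and liver criteria are tail criteria, for which cut measures are well suited.

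**Conclusion.** The point holds as a gap in the primary safety comparison. Changes from baseline in laboratory, ECG and vital-sign values have no planned between-arm estimate with an interval, and the stated reason for withholding intervals does not cover them. For a 0.5 SD shift shared by most subjects, the CI excludes zero in 23-36% of trials on the cut scale, 60% for the mean difference and 72% with baseline adjustment. These figures rest on normal changes, cuts at 10-20%, and an assumed correlation of 0.5; the documents give no SD, so the shift cannot be put in clinical units. If the effect is confined to a minority with large rises, the gain is small, absent or reversed. The continuous intervals should therefore be added beside the AE and PDLC intervals, not put in their place. The change is worth making because it serves the stated objective at almost no cost, but the plan is not internally inconsistent without it.

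**What to change.** In Table 27, add a descriptive 95% CI for the MK-5592 minus voriconazole difference in change from baseline for a short prespecified list, for example QTc, ALT, AST, total bilirubin, creatinine, potassium and magnesium. Estimate it at scheduled visits (for example Day 8, Day 42 and EOT/discontinuation) by ANCOVA or a repeated-measures model with baseline value and disease stratum as covariates, on the log scale for enzymes, bilirubin and creatinine. Keep the by-arm summaries and the AE and PDLC intervals as planned.

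Use scheduled-visit values, including the discontinuation visit, and not each subject's worst post-baseline value. A maximum grows with the number of visits, so unequal withdrawal alone creates a difference. Assuming 10 visits (3 if withdrawn), within-subject correlation 0.5 and withdrawal of 10% v 30-40%, the spurious difference is about 0.10-0.15 SD, and the CI falsely excludes zero in 8-12% of trials instead of 5%. A worst value also has no single direction for potassium or magnesium.

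The cost is SAP wording and one extra table from data already collected. The downside is a few more unadjusted intervals, of a kind the plan already labels descriptive.
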